5.2 General Concomitant Medication and Supportive Care Guidelines

5.2.1 Prohibited Concomitant Medications

Potential for Drug Interactions

Because there is a potential for interaction of ARQ 197 (tivantinib) with other concomitantly administered drugs through the cytochrome P450 system (see Section

2.2.1), the case report form must capture the concurrent use of all other drugs, over-the-counter medications, or alternative therapies. The Principal Investigator should be alerted if the patient is taking any agent known to affect or with the potential to affect selected CYP450 isoenzymes. Appendix D presents an information sheet for patients to alert them and their caregivers of any medication changes.

Since ARQ 197 (tivantinib) is metabolized by CYP2C19 and CYP3A4, a potential for drug-drug interaction exists when ARQ 197 (tivantinib) is co-administered with drugs that are CYP2C19 inhibitors/inducers or strong CYP3A4 inhibitors. Use of such drugs is permissible, but investigators should use caution and be aware that ARQ 197 (tivantinib) exposure may be altered when concomitantly administering these drugs. No additional laboratory tests are required, but it is expected that side effects as listed in this protocol for tivantinib could potentially be more pronounced.

5.2.1.1 Other Investigational Drug Therapies

Patients may not receive any other investigational drugs while on study drug.

5.2.1.2 Anticancer Therapies

No other anticancer therapies may be administered to patients while they are on study drug. These include but are not limited to chemotherapy, radiotherapy, hormonal therapy (except megestrol acetate as supportive care), immunotherapy, or locoregional therapy.

5.2.1.3 Immunosuppressive therapies

Patients may not receive any immunosuppressive therapies while on study drug.

5.2.2 **Permitted Concomitant Medications**

Standard therapies

Standard therapies for concurrent medical conditions are allowed.

5.2.3. Erythropoietin Stimulating Agents (ESA)

Please follow ASCO or MEDICARE guidelines for the use of ESA in patients diagnosed with cancer, drug labels and the Food and Drug Administration (FDA) alerts dated March 9, 2007; November 8, 2007; March 12, 2008; July 31, 2008; and December 2, 2008. **We generally discourage routine use of ESAs and use should be reserved to patients, who are clinically symptomatic.**

Hematopoietic growth factors

ASCO guidelines should be followed for the use of hematopoietic growth factors, including filgrastim or other colony-stimulating factors.

Antiemetics

Prophylactic and supportive antiemetics may be administered according to common practice.

5.2.4. **Precautions, Warnings, and Other Supportive Care Guidelines**

Myelosuppression

Myelosuppression (anemia, neutropenia, febrile neutropenia, thrombocytopenia, leukopenia, and lymphopenia) has been reported in single agent and combination therapy clinical trials of ARQ 197 (tivantinib). Complete blood count should be performed weekly or every other week. Caution is advised when any CYP2C19 inhibitors and/or strong CYP3A4 inhibitors are used as concomitant therapy. More frequent hematology testing and prophylactic use of hematopoietic growth factors is advised according to ASCO guidelines. The incidence of myelosuppression is higher in patients with HCC. Subjects with HCC or patients who experience neutropenia should be monitored more closely throughout the study and follow dose modifications or delays as specified in the protocols.

Bradycardia

Bradycardia has been reported in single agent and combination therapy clinical trials of ARQ 197 (tivantinib). In general, these events were mild to moderate in severity and asymptomatic, and subjects recovered without additional therapy. ARQ 197 (tivantinib) should be used with caution in patients who have or who are at significant risk of developing bradycardia. Pulse will be evaluated on day 1 of the first cycle and on subsequent visits. Additional EKGs should be performed if clinically indicated, especially if significant abnormalities of the baseline or subsequent EKGs are present.

Other

Treatment of emergent toxicities is at the investigator's discretion.

5.3 Duration of Therapy

In the absence of treatment delays due to adverse event(s), treatment may continue until one of the following criteria applies:

- Disease progression,
- Intercurrent illness that prevents further administration of treatment,
- Unacceptable adverse event(s),
- Patient decides to withdraw from the study, or
- General or specific changes in the patient's condition render the patient unacceptable for further treatment in the judgment of the investigator.
- Pregnancy

Patients treated with cetuximab as a single agent will have the opportunity to receive ARQ 197 (tivantinib) after progressive disease (PD) (*see schema at beginning of protocol*).

5.4 Duration of Follow Up

Patients will be followed for any medical issues for a minimum of **8 weeks (6 months)** is recommended) after removal from study or until death, whichever occurs first. Patients removed from study for unacceptable adverse events will be followed until resolution or stabilization of the adverse event. In addition patients will be followed for **survival 5 years post treatment or until death**, whichever occurs first. Information on progression (as defined in this protocol) or death will be collected even if the patient has been removed from the study previously.

5.5 Criteria for Removal from Study

Patients will be removed from study when any of the criteria listed in Section 5.3 applies. The reason for study removal and the date the patient was removed must be documented in the Case Report Form.

Patients may be discontinued from trial treatment and assessments at any time, at the discretion of the investigator(s). In addition to the above listed criteria additional specific reasons for discontinuing a patient from this trial are:

- patient lost to follow-up (i.e., dropouts)
- protocol non-compliance

If the reason for withdrawal from the trial is the death of the patient, the two options for categorizing withdrawal are either progressive disease or an adverse event (AE). More than one AE may be documented as a reason for withdrawal. Only one event will be captured as the cause of death. Note that death is an outcome and not an adverse event.

All deaths that occur within the trial period or within 30 days after administration of the last dose of trial drug must be reported to NCI primarily for the purposes of serious adverse event (SAE) reporting. However, deaths unequivocally related to progression are not SAEs. All subjects who have new or worsening CTC grade 3 / 4 laboratory values (CTCAE 4.0) at the time of withdrawal must have further tests performed and the results recorded appropriately until the lab values have returned to CTC grade 1 or 2, unless these values are not likely to improve because of the underlying disease. In these cases, the investigators must record their opinions in the subject's medical records. Laboratory abnormalities should **not** be reported as adverse events unless they meet criteria for a SAE, or the laboratory abnormality causes the subject to discontinue from the study, or the investigator insists the abnormality should be reported as an AE.

At withdrawal all on-going study-related toxicities and SAEs must be followed until resolution, unless in the investigator estimates that the condition is unlikely to resolve due to the subject's underlying disease.

After withdrawal from treatment, subjects must be followed up for all existing and

new AEs for 30 days after the last dose of ARQ 197 (tivantinib) and/or cetuximab. All new AEs occurring during that period must be reported to NCI and all study-related toxicities and SAEs must be followed up until resolution if possible.

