7.4.3 Expedited Reporting Guidelines

Use the NCI protocol number and the protocol-specific patient ID assigned during trial registration on all reports.

Note: A death on study requires both routine and expedited reporting

regardless of causality, unless as noted below. Attribution to treatment or other cause must be provided.

*Death due to progressive disease should be reported as **Grade 5 “Neoplasms benign, malignant and unspecified (incl. cysts and polyps) - Other (Progressive Disease)”** under the system organ class (SOC) of the same name. Evidence that the death was a manifestation of underlying disease (e.g., radiological changes suggesting tumor growth or progression: clinical deterioration associated with a disease process) should be submitted.*

Expedited Reporting Requirements for Adverse Events that Occur on Studies under an IND/IDE within 30 Days of the Last Administration of the Investigational Agent/Intervention^{1,2}

FDA REPORTING REQUIREMENTS FOR SERIOUS ADVERSE EVENTS (21 CFR Part 312) NOTE: Investigators MUST immediately report to the sponsor (NCI) ANY Serious Adverse Events, whether or not they are considered related to the investigational agent(s)/intervention (21 CFR 312.64) An adverse event is considered serious if it results in ANY of the following outcomes:
 
 1) Death 2) A life-threatening adverse event 3) An adverse event that results in inpatient hospitalization or prolongation of existing hospitalization for ≥ 24 hours 4) A persistent or significant incapacity or substantial disruption of the ability to conduct normal life functions 5) A congenital anomaly/birth defect. 6) Important Medical Events (IME) that may not result in death, be life threatening, or require hospitalization may be considered serious when, based upon medical judgment, they may jeopardize the patient or subject and may require medical or surgical intervention to prevent one of the outcomes listed in this definition. (FDA, 21 CFR 312.32; ICH E2A and ICH E6). 				

ALL SERIOUS adverse events that meet the above criteria MUST be immediately reported to the NCI via CTEP-AERS within the timeframes detailed in the table below.
				
Hospitalization	Grade 1 Timeframes	Grade 2 Timeframes	Grade 3 Timeframes	Grade 4 & 5 Timeframes
Resulting in Hospitalization ≥ 24 hrs	10 Calendar Days			24-Hour 5 Calendar Days
Not resulting in Hospitalization ≥ 24 hrs	Not required	10 Calendar Days		

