7.5 Routine Adverse Event Reporting

All Adverse Events **must** be reported in routine study data submissions. **AEs reported through CTEP-AERS must also be reported in routine study data submissions.**

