12.1 Data Reporting

12.1.1 Method

This study will be monitored by the Clinical Data Update System (CDUS) version 3.0. Cumulative CDUS data will be submitted quarterly to CTEP by electronic means. Reports are due January 31, April 30, July 31, and October 31. Instructions for submitting data using the CDUS can be found on the CTEP web site (<http://ctep.cancer.gov>). **Note:** All adverse events that have occurred on the study, including those reported through CTEP-AERS, must be reported via CDUS.

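### Section 5.5 by default keeps laboratory abnormalities out of adverse event reporting, in conflict with Sections 7 and 12.1.1, so non-serious cytopenias that lead only to a tivantinib hold or dose reduction may go unrecorded

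*Combined protocol and SAP*

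**What the plan says.** Section 5.5 sets a default with three exceptions. Abnormal laboratory findings are not to "be reported as adverse events unless they meet criteria for a SAE". That is the first exception. The second covers a finding that makes the patient leave the study. The third applies where "the investigator insists the abnormality should be reported as an AE", and it carries no grade or other criterion. The same section also says, of the 30 days after the last dose, "All new AEs occurring during that period must be reported to NCI".

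Elsewhere the protocol makes no laboratory exception. Section 7.5 requires that all adverse events "be reported in routine study data submissions". Section 12.1.1 says: "All adverse events that have occurred on the study, including those reported through CTEP-AERS, must be reported via CDUS". Section 7.3 adopts CTCAE 4.0 for adverse event reporting. The tivantinib risk list in Section 7.1.1.1 names anemia and decreased neutrophil, lymphocyte and white-cell counts as adverse events possibly related to the drug.

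On deaths, Section 5.5 states that "deaths unequivocally related to progression are not SAEs". Section 7.4.3 counts death among the serious outcomes, states "A death on study requires both routine and expedited reporting" (with a qualification), and codes death from progression as a Grade 5 event.

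**The concern.** The same abnormal count is an adverse event under Section 7 and, by default, not one under Section 5.5. Two sites could each follow the protocol and record different things.

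The events most exposed are those the protocol itself treats as important. Section 5.2.4 names myelosuppression as a precaution. Section 6 uses neutrophil and platelet counts to decide when tivantinib is held or reduced. In the phase 1 combination with erlotinib, the study closest to this one, the single dose-limiting toxicity reported was neutropenia (Section 2.2.4).

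The safety description of the combination is at stake, and possibly the early safety looks in Section 13.2. Assignment is open (Section 13.6), so recording that depends on the investigator's insistence could differ between arms.

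**Working it through.** The plan has no figure on this point to reproduce. The check is a comparison of texts, followed by two illustrations of size.

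**1. Follow one event through the protocol.** Take a non-serious grade 3 neutropenia that recovers and leads only to a tivantinib hold or a reduced dose.

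| Section | Treatment of this event |
|---|---|
| 6 and Table 6-1 | Tivantinib is withheld; it resumes at the same or a lower dose level depending on duration and recurrence |
| 7.1.1.1, risk list | Decreased neutrophil count is a listed adverse event |
| 7.1.1.1, exceptions to expedited reporting | Decreased neutrophils are exempt through grade 4 (anemia through grade 3), so routine reporting is the route left |
| 7.3 | Graded by CTCAE 4.0 |
| 7.5 and 12.1.1 | All adverse events are reported, with no laboratory exception |
| 5.5, serious-event exception | Not met, because the event is non-serious by construction |
| 5.5, discontinuation exception | Not met, because a hold or reduction is not discontinuation from the study |
| 5.5, investigator exception | Met only if the investigator insists |

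Section 5.5 therefore narrows the one reporting route that Section 7 leaves open for this event.

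**2. How many patients could be affected.** The denominator is 38 combination patients (Section 13.2). The rates are drug-related neutropenia in Section 2.2.4. Expected count = 38 × rate.

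- Tivantinib plus erlotinib (ARQ 197-111), 6.3%: 38 × 0.063 = 2.4
- Liver cancer, placebo-controlled (ARQ 197-215), 16.3%: 38 × 0.163 = 6.2
- Liver cancer with cirrhosis (ARQ 197-114), 42.9%: 38 × 0.429 = 16.3

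The range is about 2 to 16 patients with any drug-related neutropenia. It is an upper frame for what could be missed, because serious events, events causing discontinuation and events the investigator chooses to report would still be recorded.

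**3. The early safety look.** Section 13.2 lets the trial continue if fewer than 2 of 6 combination patients have severe toxicity. If the look counts recorded adverse events, the chance of reaching 2 or more at recorded rate p is 1 − (1 − p)^6 − 6p(1 − p)^5. The rates below are assumptions, not figures from the documents.

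- p = 0.30 (assumed true rate, fully recorded): 1 − 0.118 − 0.303 = 0.58
- p = 0.20 recorded: 1 − 0.262 − 0.393 = 0.34
- p = 0.15 recorded: 1 − 0.377 − 0.399 = 0.22
- p = 0.10 recorded: 1 − 0.531 − 0.354 = 0.11 (unrounded 0.114)

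If half of a true 30% rate went unrecorded, the chance of flagging it would fall from 0.58 to 0.22.

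**The case against.** The strongest reply is that the texts can be read together: Sections 7.5 and 12.1.1 say that adverse events must be reported, and Section 5.5 says which laboratory findings count as adverse events. The sentence also stands in a paragraph about withdrawal. This helps with 7.5 and 12.1.1 taken alone. It does not remove the conflict with CTCAE grading or with a risk list that names blood-count decreases as adverse events, and the sentence is worded generally, so a site could apply it throughout treatment.

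It is also fair that much is still captured. Serious events and discontinuations remain reportable. Delays beyond two weeks, failed recovery and grade 4 thrombocytopenia lead under Section 6 to stopping tivantinib or leaving protocol therapy, and can be taken to meet the discontinuation exception. Grade 3 or 4 values at withdrawal are followed and recorded, and blood counts and chemistry are done on schedule. The exposed group is therefore temporary holds, dose reductions and milder changes.

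Several stronger readings are tempting, and the documents do not support them:

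- **That the rule hides the main toxicity of tivantinib.** In the risk list (756 patients) fatigue is the only event above 20%; the blood-count terms are at 20% or below.
- **That 6 to 16 of 38 patients is the likely range.** Those figures come only from liver cancer studies, and Section 5.2.4 says myelosuppression is more frequent there. The erlotinib combination gives about 2.
- **That most neutropenia would go unreported, because Section 2.2.4 lists 29 neutropenia and 4 febrile neutropenia events.** That paragraph gives a total of 58, while its components sum to 65 + 29 + 17 + 13 + 11 + 4 = 139, and it does not say which events were serious.
- **That hypomagnesemia adds to an imbalance against the combination.** Section 6.2 treats it as a cetuximab effect, and both arms receive cetuximab.
- **That a between-arm toxicity test would be biased.** Section 13 specifies no such test.

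**Conclusion.** The conflict is real and lies in a stated rule, not in missing detail. It should be corrected. Followed literally, Section 5.5 leaves non-serious cytopenias that cause only a hold or dose reduction to the discretion of an unblinded investigator, so a principal dose-modifying toxicity of tivantinib would be under-recorded in the safety results.

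The illustrative size, about 2 to 16 of 38 combination patients with drug-related neutropenia, assumes that rates from other populations carry over. The share that would actually be lost is unknown. The effect on the 3- and 6-patient looks holds only if those looks rely on recorded adverse events, which Section 13.2 does not say. The efficacy sample size is untouched. The direction and size of any between-arm difference in recording cannot be established from the documents.

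The wording on progression deaths is a secondary inconsistency in classification. A reader might infer that such deaths could go unreported. They would not: Section 5.5 itself sends all deaths during the trial or within 30 days of the last dose to NCI, and Section 7.4.3 tells sites how to code progression deaths.

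**What to change.** Remove the laboratory sentence from Section 5.5. Alternatively, replace it with a reference to Section 7.5 and a stated CTCAE 4.0 grade from which laboratory abnormalities are recorded as adverse events in both arms. In either case, always record any laboratory abnormality that leads to a hold or dose change, whatever its grade. State in Section 13.2 which data the 3- and 6-patient looks use.

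Reconcile the progression-death statement in Section 5.5 with Section 7.4.3, for example by replacing it with a reference to that section.

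The cost is protocol wording and additional form entries. No new tests are needed, because counts and chemistry are already on the study calendar. With weekly counts and a 17-item chemistry panel through week 10, recording every grade could produce many minor entries. This is the reason to prefer a stated grade threshold if workload is a concern.

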6. DOSING DELAYS/DOSE MODIFICATIONS

Dose Level	Tivantinib Dose
Starting Dose	360 mg, po, twice a day
-1	240 mg, twice a day
-2	120 mg, twice a day

Up to two dose reductions are acceptable. Persistent toxicities in spite of two dose reductions will result in discontinuation of therapy.

Event Name	Non-hematological toxicities	
Grade of Event	Management/Next Dose for ARQ 197 (tivantinib)	Management/Next Dose for Cetuximab
≤ Grade 1	Continue therapy	Continue therapy. See 6.2
Grade 2	Continue therapy	Continue therapy. See 6.2
Grade 3*	If at least possibly related to ARQ 197 (tivantinib) and not amenable to an established, rapidly effective treatment**: hold ARQ 197 (tivantinib) until resolution to ≤Grade 2	If at least possibly related to cetuximab and not amenable to an established, readily effective treatment**: hold cetuximab until resolution to ≤Grade 2. See 6.2
Grade 4*	If at least possibly related to ARQ 197 (tivantinib) and not amenable to an established, rapidly effective treatment**: hold ARQ 197 (tivantinib) until resolution to ≤Grade 2	If at least possibly related to cetuximab and not amenable to an established, readily effective treatment**: hold cetuximab until resolution to ≤Grade 2. See 6.2
* Treating Physician to assess relatedness and impact on patient health		
** E.g. adverse events that are readily addressed with additional therapy typically within 24 hours – e.g. pain medication for increased pain or insulin for increase blood glucose level.		
Patients requiring a delay of >2 weeks should go off protocol therapy. Patients requiring > two dose reductions should go off protocol therapy.		
Recommended management: For vomiting : antiemetics. For diarrhea : Loperamide antidiarrheal therapy. Dosage schedule: 4 mg first onset, followed by 2 mg with each loose motion until diarrhea-free for 12 hours (maximum dosage: 16 mg/24 hours). Adjunct anti-diarrheal therapy is permitted and should be recorded when used.		

Event Name	Hematological Toxicities***
------------	-----------------------------

Grade of Event	Management/Next Dose for ARQ 197 (tivantinib)	Management/Next Dose for Cetuximab
Grade 1	No change in dose	No change in dose
Grade 2	No change in dose	No change in dose
≥ Grade 3 neutropenia recovering within 5 days	Withhold ARQ 197 (tivantinib) If ANC recovers to $\geq 1.5 \times 10^9/L$ ($\geq 1500/mm^3$) within 5 days, resume treatment with ARQ 197 (tivantinib) at the same dose level. For subsequent dose delays resume at one dose level lower.**	Continue therapy if deemed appropriate by the treating physician
≥ Grade 3 neutropenia lasting >5 days or ≥ Grade 3 febrile neutropenia	Withhold ARQ 197 (tivantinib) for up to 14 days.* If ANC recovers to $\geq 1.5 \times 10^9/L$ ($\geq 1500/mm^3$) within 14 days, treatment with ARQ 197 (tivantinib) should resume at a dose that is decreased by one dose level for subsequent cycles.** If ANC does not recover to $\geq 1.5 \times 10^9/L$ ($\geq 1500/mm^3$) within 14 days after interrupting ARQ 197 (tivantinib), discontinue administration of ARQ 197 (tivantinib).	Continue therapy if deemed appropriate by the treating physician
Platelet count $< 50 \times 10^9/L$ ($< 50,000/mm^3$)	Withhold ARQ 197 (tivantinib) for up to 14 days. If platelet count recovers to $\geq 100 \times 10^9/L$ ($\geq 100,000/mm^3$) within 14 days, resume treatment with ARQ 197 (tivantinib) at same dose level.* If a second dose delay is required for the same event, then decrease	Continue therapy if deemed appropriate by the treating physician

	ARQ 197 (tivantinib) dose by one dose level for subsequent cycles**. If platelet count does not recover to $\geq 100 \times 10^9/L$ ($\geq 100,000/mm^3$) within 14 days after interrupting ARQ 197 (tivantinib), discontinue ARQ 197 (tivantinib) administration.	
Grade 4 thrombocytopenia	Discontinue administration of ARQ 197 (tivantinib).	Discontinue treatment
*Patients requiring a delay of >2 weeks should go off protocol therapy.		
**Patients requiring > two dose reductions should go off protocol therapy.		
***Felt to be at least possibly related to ARQ 197 (tivantinib) treatment		
Growth factor support with e.g. G-CSF is acceptable as indicated		

